### Hypotheses

Correct identification of NNS-containing products (co-primary outcome): We predict that, compared to the control arm, correct identification of NNS-containing products will be higher for participants assigned to the Chilean NNS label arm or to the Colombian NNS label arm (H1).

Selection of NNS-sweetened product (co-primary outcome): We predict that, compared to the control arm, selection of the NNS-sweetened product will be lower for participants assigned to the Chilean NNS label arm or to the Colombian NNS label arm (H2).

Selection of unsweetened product (co-primary outcome): We predict that, compared to the control arm, selection of the unsweetened product will be higher for participants assigned to the Chilean NNS label arm or to the Colombian NNS label arm (H3).

Selection of sugar-sweetened product (secondary outcome): We predict that, compared to the control arm, selection of the sugar-sweetened product will not differ for participants assigned to the Chilean NNS label arm or to the Colombian NNS label arm (H4).

Perceived message effectiveness (secondary outcome): We predict that, compared to the control arm, the perceived message effectiveness (PME) of the labels will be higher for participants assigned to the Chilean NNS label arm or to the Colombian NNS label arm (H5).

Perceived product healthfulness (secondary outcome): We predict that, compared to the control arm, perceived product healthfulness will be lower for participants assigned to the Chilean NNS label arm or to the Colombian NNS label arm (H6).

Perceived relative product healthfulness (secondary outcome): We predict that, compared to the control arm, perceived relative product healthfulness will be lower for participants assigned to the Chilean NNS label arm or to the Colombian NNS label arm (H7).

Intentions to limit NNS consumption (secondary outcome): We predict that, compared to the control arm, intentions to limit their child's NNS consumption will be higher for participants assigned to the Chilean NNS label arm or to the Colombian NNS label arm (H8).

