## Main Analyses

We will use a two-sided critical alpha of 0.05 to conduct all statistical tests. All confidence intervals presented will use a 95% confidence level. Analyses of the primary and secondary outcomes will include all participants according to the trial arm to which they were randomized.

For all selection/identification tasks, we will code outcomes dichotomously. For correct identification of NNS-containing products, we will dichotomize the outcome to correct identification of NNS-containing products (coded as 1) vs. incorrect identification (coded as 0). Correct identification will be defined as having identified the two NNS-containing products in the set and no other products, while incorrect identification will be defined as any other scenario. For selection of NNS-sweetened product, we will dichotomize the outcome to selection of one of two NNS-sweetened products (coded as 1) vs. selection of either of the two non-NNS-sweetened products (coded as 0). For selection of unsweetened product, we will dichotomize the outcome to selection of the unsweetened product (coded as 1) vs. selection of any of the other three products (coded as 0). For selection of sugar-sweetened product outcome, we will dichotomize the outcome to selection of one of the two sugar-sweetened products (coded as 1) vs. selection of either of the other two non-sugar-sweetened products (coded as 0).

For dichotomous outcomes, we will first descriptively report unadjusted proportions in each experimental arm, including proportions for each product category and for all product categories simultaneously (e.g., whether the participant correctly identified the

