NNS-containing products in all three product categories). Next, to test H1-H4, we will use logistic mixed-effects regression models, treating the intercept as random to account for repeated measures within participants. Models will regress each outcome on indicator variables for the experimental arms, product categories, and their interactions. After model estimation, we will test the joint statistical significance of the interaction terms, and, if not significant, we will drop the interactions from the models. Regardless of the presence of the interaction terms in the final model, we will obtain the predicted probabilities of each outcome by experimental arm for each separate product category, which we will use to conduct a joint test of statistical significance of the differences in predicted probabilities across product categories. If such differences are jointly significant, we will report average differential effects (ADEs) of each type of NNS label (i.e., differences in predicted probabilities between each NNS label type and the control label) separately for each product category. Alternatively, if differences are not jointly significant, we will report ADEs of each type of NNS label across product categories.

For the PME outcome, we will verify that Cronbach's alpha is sufficient ( $>0.7$ ) and average each participant's scores across the three PME items. If Cronbach's alpha is not sufficient ( $<0.7$ ), we will treat each item as a separate construct instead. Next, for all continuous outcomes, we will descriptively report unadjusted means in each experimental arm, including means for each product category and averaged across all product categories. To test H5-H8, we will use linear mixed-effects regression models. Models will regress the outcomes on indicator variables for experimental arms, product category, and their interactions. After model estimation, we will test the joint statistical significance of the interaction terms. If the interactions are jointly significant, we will keep them in the models and report ADEs of each type of NNS label (i.e., differences in predicted means between each NNS label type and the control label) separately for each product category. Alternatively, if the interactions are not jointly significant, we will drop them from the models and report ADEs of each type of NNS label across product categories.

We will use complete case analysis to handle any missing data.

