## **Exploratory Analyses**

Post estimation of each main analytic model, we will obtain exploratory comparisons between the outcomes in the two NNS label arms.

Additionally, we will examine whether gender and/or educational attainment moderates the effects of the NNS labels (compared to control) on the co-primary outcomes. If there are no significant differences in ADEs by product category in the main analyses, moderation analyses will use logistic mixed-effects models with random intercepts including indicator variables for experimental arms, the moderator, and their interactions. If, alternatively, there are significant differences in ADEs by product category in the main analyses, we will use separate regression models for each product category.

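### For H1-H4, the test that chooses pooled or category-specific effects is run after non-significant interactions are dropped, so it is valid only if one common odds ratio holds per label.

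*Combined protocol and SAP*

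**What the plan says.** All of this concerns the dichotomous outcomes H1-H4 under Main Analyses. The model is a random-intercept logistic regression on arm, product category and their interaction.

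- First test: the interaction terms are tested jointly and, "if not significant, we will drop the interactions from the models".
- Second test: "Regardless of the presence of the interaction terms in the final model, we will obtain the predicted probabilities of each outcome by experimental arm"; there is one such set per product category. These are the probabilities which "we will use to conduct a joint test of statistical significance of the differences in predicted probabilities across product categories".
- Consequence: if that test is significant, ADEs are reported for each category separately; "if differences are not jointly significant, we will report ADEs of each type of NNS label across product categories". An ADE is defined there as "differences in predicted probabilities between each NNS label type and the control label".

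Exploratory Analyses relies on the result: if "there are significant differences in ADEs by product category in the main analyses, we will use separate regression models for each product category" in the moderation analyses.

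The hypotheses do not mention category. H1, for example, predicts that "correct identification of NNS-containing products will be higher for participants assigned to the Chilean NNS label arm or to the Colombian NNS label arm". For H5-H8 there is no second test; the interaction test alone decides.

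**The concern.** After the interactions are dropped, the model has one log-odds effect per label and no parameter that lets a label act differently on fruit drinks, yogurts and cereals. Its ADEs can still differ by category, but only because equal odds ratios at unequal base rates give unequal probability differences. The size and direction of the differences are imposed by the model, and their standard errors reflect that imposition.

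Three things are at stake:

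- whether the overall ADE for co-primary H1-H3 is reported, since the plan gives it only when the second test is non-significant;
- whether label effects are said to differ by category, and in which order;
- whether the exploratory moderation models are split by category for the outcome concerned.

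The wording adds a second difficulty. Taken literally, the test compares predicted probabilities across categories. Exploratory Analyses describes the same result as a difference in ADEs. These are different hypotheses.

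**Working it through.** **Inputs from the documents.** Two-sided alpha 0.05 (Main Analyses); 1,102 per arm and the arm-level rates (Sample Size and Power). From those tables, control to label: at the 60% assumption, H2 is 50% to 26.7%, H3 30% to 60%, H4 40% to 26.7%; at the 90% assumption, H2 is 50% to 6.7%, H3 45% to 90%, H4 10% to 6.7%.

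**Assumed.** Spread of control rates over the three categories (highest minus lowest) 3, 5 or 10 points; random-intercept SD 1.0 or 1.8; both labels equally effective; a generic 35% to 45% effect, since H1 has no stated rates.

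**The plan's own figure.** n = [1.96·√(2p̄q̄) + 0.8416·√(p₁q₁ + p₂q₂)]² / (p₁ − p₂)². With 0.10 and 0.067, p̄ = 0.0835 and n = (0.7668 + 0.3287)² / 0.033² = 1,102. This agrees with the plan; it only sets n here.

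**Why the first test does not protect the second.** Take control rates 30/35/40% and add exactly 10 points in each. The odds ratios are

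- (0.40/0.60)/(0.30/0.70) = 1.56
- (0.45/0.55)/(0.35/0.65) = 1.52
- (0.50/0.50)/(0.40/0.60) = 1.50

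Equal ADEs thus imply slightly unequal odds ratios. The interaction test rarely detects so small a difference: it was non-significant in about 94% of simulated trials. The reduced model then forces one odds ratio and so must show unequal ADEs.

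**Why the second test then rejects.** For control rates 30/35/40% and a 10-point effect, the reduced model shows a gap of 0.7-0.8 points between lowest and highest category. Its SE is 0.14-0.15 with interactions dropped and 2.4-2.7 with them kept. The ratios are roughly 0.75/0.145 = 5.2 and 0.75/2.55 = 0.3.

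**Simulation of the whole sequence.** Maximum likelihood with 31-point quadrature; 4-df Wald interaction test; then a delta-method 1-df test of lowest against highest category for one label in the final model. True ADEs are equal in every row, so the nominal rate is 5%. Ranges cover both SDs and repeated runs of 250 to 4,000 trials.

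| Scenario | Spread | Declared different | Mean false gap when dropped |
|---|---|---|---|
| 35% to 45% | 3 | 56-81% | 0.2 points |
| 35% to 45% | 5 | 94-97% | 0.35 points |
| 35% to 45% | 10 | 94-97% | 0.7 points |
| H4, 60% rates | 10 | 91-96% | about 2 points |
| H4, 90% rates | 5 | 81-88% | 1.7-1.9 points |
| H3, 90% rates | 5 | 44-53% | about 5 points |
| H3, 90% rates | 10 | about 5% | rarely dropped |
| H2, 90% rates | 5 / 10 | 10-12% / 4-6% | rarely dropped at 10 |
| No label effect | 10 | 2-7% | none |

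With interactions kept, the same contrast rejects in 3-6% of trials, apart from sampling noise in the smaller runs.

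**Direction.** If the true ADE falls by 4 points while control rates rise by 10 (mean 35% to 45%), the sequence reports a significant rise in about 57-70% of trials.

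**Literal reading.** With no label effect and mean rates of 35% or 50%, category-specific reporting follows in 68-81% of trials at a 3-point spread and 99-100% at 5 or 10.

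**Moderation.** Splitting one outcome turns 2 models (one per moderator) into 6. Each label contrast then has an SE √(3/(1+2r)) times the pooled one, where r is the between-category correlation: 1.50 at r = 0.17 (SD 1.0) and 1.33 at r = 0.35 (SD 1.8).

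**The case against.** The second test may be deliberate. ADEs are on the probability scale, where a common odds ratio with unequal base rates does give unequal ADEs, and rejecting is then correct. A reader might infer that the reduced-model test can never separate equal from unequal label effects. The plan does not support that: with a common odds ratio, a joint version of the test rejected in 0.5% of trials at equal base rates and 100% at 10/25/45%. What stands is that the test needs the common odds ratio and the plan does nothing to establish it.

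A reader might also infer that base rates alone trigger category-specific reporting. That holds only on the literal reading, which is the weaker one, given the ADE definition in the next sentence and the description in Exploratory Analyses. It supports a wording correction only.

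The plan calls its test joint but does not define it. With two labels and three categories it would have 4 df, which is near-singular in the reduced model. The 1-df test above is a stand-in, and the percentages would vary with implementation. A joint two-label version, run at control rates 20/30/40% with a true ADE of 5 points throughout, led to category-specific reporting in 83-95% of trials, so the result does not hinge on the 1-df choice.

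The false gaps are often under one point, and category proportions are promised anyway: "we will first descriptively report unadjusted proportions in each experimental arm, including proportions for each product category". Both points stand and limit the harm.

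**Conclusion.** The concern holds on the ADE reading. In the reduced model the second test rests on a common odds ratio that a non-significant interaction test does not establish, and it can declare equal ADEs unequal far more often than 5%.

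The size depends on base rates that the documents do not give. The error is near-certain but numerically small around 35% to 45%. It is larger in points for H4, and for H3 at the 90% rates with a 5-point spread. It largely disappears for H2 and H3 at the 90% rates with a 10-point spread, where the first test keeps the interactions, and it is absent when the labels have no effect.

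Two stronger inferences are not supported. The conclusions on H1-H3 are not shown to be wrong: the reduced model still gives one coefficient per label, and the verdict per label is usually unchanged. Nor do all the moderation analyses necessarily split: six models become 18 only if the test is significant for all three co-primary outcomes. The change should be made before data collection, but it does not undermine the trial.

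**What to change.** In Main Analyses, for each label and each of H1-H4:

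1. Always report, as the main result, the ADE averaged with equal weight over the three product categories. Give category-specific ADEs from the interaction model as secondary.
2. Replace the second test with one named test: a joint 4-df Wald test that each label's ADE is equal across the three categories, for both labels together, computed in the model that keeps the interactions. State that it concerns ADEs, not predicted probabilities.
3. In Exploratory Analyses, make the condition for separate models refer to that test.

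The cost is SAP wording, one averaged contrast per model and slightly more reporting; no extra data. The averaged ADE loses no precision: in the 30/35/40% example its SE is the same with interactions kept or dropped (1.38 points at SD 1.0, 1.55 at SD 1.8).

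The real downside is a less sensitive heterogeneity test when a common odds ratio truly holds. For H2-H3 at the 90% rates, true gaps of 5.7-7.2 points would be detected in 61-88% of trials (98-100% as now written) and gaps of 2.9-3.6 points in 18-30% (82-95% as now written).

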## **Exploratory Analyses**

Post estimation of each main analytic model, we will obtain exploratory comparisons between the outcomes in the two NNS label arms.

Additionally, we will examine whether gender and/or educational attainment moderates the effects of the NNS labels (compared to control) on the co-primary outcomes. If there are no significant differences in ADEs by product category in the main analyses, moderation analyses will use logistic mixed-effects models with random intercepts including indicator variables for experimental arms, the moderator, and their interactions. If, alternatively, there are significant differences in ADEs by product category in the main analyses, we will use separate regression models for each product category.

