### Study Protocol

Participants will complete an online randomized experiment programmed in Qualtrics. After providing informed consent, participants will be randomly assigned to view 1 of 3 types of labels: a neutral control label, a text NNS warning label (i.e., Chilean NNS label), or an octagonal NNS warning label (i.e., Colombian NNS label).

First, participants will view their assigned label on four similar products (one unsweetened, one sweetened with sugar, one sweetened with NNS, and one sweetened with both sugar and NNS) displayed in random order. They will then complete a task in which they select one of the products to purchase for their child and identify which of the products contain NNS. During this task, in all experimental arms, products will also display Chile's current "high in sugar" and "high in calories" labels when applicable. This task will be repeated 3 times, each time with a different product category (i.e., fruit drinks, yogurts, breakfast cereals), with categories displayed in random order.

Next, participants will view their assigned label on two products containing NNS (i.e., flavored milk and cereal bar). For each product, participants will rate the perceived message effectiveness of the label, perceived product healthfulness, and perceived relative product healthfulness.

Lastly, after all product exposures, participants will rate their intentions to limit their child's NNS consumption.

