Therefore, to be conservative, we assumed that 90% of participants would prefer unlabeled products over comparable products with warning labels, and the remaining 10% would be indifferent between comparable products with different numbers of warning labels. Based on these assumptions, a sample of 1,102 participants per arm (3,306 total) provides 80% power to detect differences between the control arm and each NNS label arm, using two-sided two-sample proportions tests with a critical alpha of 0.05.

Given the use of repeated measures, this required sample size further assumes that respondents will not choose differently across product categories – i.e., that 1,102 is the effective sample size. This is a conservative assumption, as within-participant variation would increase the effective sample size, thereby reducing the number of participants required.

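### Exploratory moderation analysis: splitting into three one-response models leaves no overall moderation test and no test of whether moderation differs by category, and the pooled version drops product category

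*Combined protocol and SAP*

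**What the plan says.** The Study Protocol section gives each participant three selection and identification tasks: "This task will be repeated 3 times, each time with a different product category". The main model for the dichotomous outcomes keeps these together in a random-intercept logistic regression: "Models will regress each outcome on indicator variables for the experimental arms, product categories, and their interactions" (Main Analyses).

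The Exploratory Analyses section then sets two routes for moderation by gender and by education on the three co-primary outcomes:

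- If ADEs do not differ significantly by category, a pooled random-intercept model is fitted, "including indicator variables for experimental arms, the moderator, and their interactions". Product category is not in that list.
- If they do differ, "we will use separate regression models for each product category".

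On error rates, the Main Analyses section says only: "We will use a two-sided critical alpha of 0.05 to conduct all statistical tests". No multiplicity adjustment and no power figure is given for moderation.

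**The concern.** The rule that chooses the route looks at whether label effects vary by category. It does not look at moderation. A label effect that is larger for yogurts than for cereals does not imply that gender changes the label effect differently for yogurts and cereals. Yet once the rule is met, the analysis gives up the joint model.

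Three consequences follow. First, no single result answers whether gender or education moderates the label effect. Second, if one category is significant and another is not, readers may infer category-specific moderation, which three separate p-values cannot test. Third, one test per label, moderator and outcome becomes three, each using a third of the available responses.

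In the pooled route, non-significant ADE differences do not mean that baseline choices are the same for drinks, yogurts and cereals. Leaving category out therefore makes the moderation model differ from the main model for no stated reason.

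**Working it through.** **Inputs from the document.** Two-sided alpha 0.05; 1,102 per arm; three responses per participant; two label-versus-control contrasts; two moderators; three co-primary outcomes. The within-participant correlation ρ is not given, so it is varied.

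**The plan's own figure.** For 0.10 against 0.067, mean 0.0835:

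n = [1.96·√(2·0.0835·0.9165) + 0.842·√(0.10·0.90 + 0.067·0.933)]² / 0.033² = 1,102 per arm.

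This agrees with the Sample Size and Power section. It concerns the main comparison for sugar-sweetened choice and says nothing about power for moderation.

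**Per-test power after the split.** Assume the same interaction in all three categories, with equal standard errors. The average of three estimates has variance σ²(1+2ρ)/3, so the single-category standard error is √(3/(1+2ρ)) times the pooled one. For an effect with 80% pooled power (1.96 + 0.84 = 2.80), single-category power = Φ(2.80/ratio − 1.96).

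| ρ | SE ratio | Power per category | Chance of ≥1 false claim in three tests |
|---|---|---|---|
| 0 | 1.73 | 37% | 14% |
| 0.2 | 1.46 | 48% | 14% |
| 0.3 | 1.37 | 53% | 14% |
| 0.5 | 1.22 | 63% | 12-13% |
| 0.7 | 1.12 | 71% | 11% |
| 1 | 1.00 | 80% | 5% |

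The last column comes from simulating three equally correlated null test statistics, each tested at 0.05.

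**Conflicting verdicts.** In the same setting (equal moderation everywhere, 80% pooled power), one or two of the three tests, but not all, are significant in 65%, 60% and 47% of trials at ρ = 0.2, 0.3 and 0.5. All three are significant in 16%, 23% and 38%.

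**Number of tests.** With two-level moderators, the pooled route has 2 labels × 2 moderators × 3 outcomes = 12 tests. The split has 12 × 3 = 36 if all three outcomes take that route. This is a maximum for two-level moderators; the number of education levels is not stated.

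**Omitting category in the pooled route.** A small simulation (12 replicates per setting) used two arms of 1,102, a 50/50 moderator, a true log-odds interaction of 0.4, a random-intercept SD of 1.2, and category shifts of ±0.5 or ±1.0 logit. All of these except the arm size are assumptions.

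| Quantity | ±0.5: with category | ±0.5: without | ±1.0: with category | ±1.0: without |
|---|---|---|---|---|
| Log-odds interaction | 0.370 | 0.353 | 0.388 | 0.321 |
| Random-intercept SD | 1.16 | 1.08 | 1.19 | 0.84 |
| Moderator difference in ADE | 0.069 | 0.069 | 0.068 | 0.068 |

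The log-odds interaction shrinks by (0.370−0.353)/0.370 ≈ 5% and (0.388−0.321)/0.388 ≈ 17%. A second simulation with 3,306 participants gave 7% (category proportions 31/45/60%) and 23% (20/45/73%), with z-values hardly changed.

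**The case against.** **The loss of power can be overstated.** A reader might infer that the split costs most of the power. The document does not support that. Every split model keeps all 1,102 participants per arm, and only the gain from repeated measures is lost. From 80% pooled power, the relative loss exceeds half only when ρ is near 0: (80−37)/80 = 54% at ρ = 0, against (80−63)/80 = 21% at ρ = 0.5. The sample-size plan takes no credit for repeated measures. It assumes that "respondents will not choose differently across product categories – i.e., that 1,102 is the effective sample size", and at ρ = 1 the loss is zero. This objection stands against the strong reading. The zero-loss case gives little comfort, however: if participants chose identically in all categories, label effects could not differ by category and the split would not arise.

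**The comparison is not like for like.** The split follows the plan's own reporting unit, since ADEs are then reported by category. An averaged test answers a different question and can do worse. If moderation sits in one category only, the average is one third as large. An effect that a single-category model detects with 80% power is then detected by the averaged test with power Φ((2.80/3)·√(3/(1+2ρ)) − 1.96), which is 28%, 25% and 21% at ρ = 0.2, 0.3 and 0.5. Even with equal moderation, at least one of the three unadjusted split tests is positive with probability of roughly 75-86%. This stands, and it is why the category-specific estimates should be kept beside the overall test.

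**Omitting category does little harm on the planned scale.** A reader might infer that the pooled route will report biased odds ratios. The plan names no odds ratios as output; it reports ADEs, which are differences in predicted probabilities. Every participant sees all three categories, so category is balanced across arms and moderator levels, and the ADE contrast is unaffected in simulation. This stands too.

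**The analysis is exploratory.** None of H1-H8 concerns moderation and no power is claimed for it. This limits the severity.

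**Conclusion.** The point holds in a limited form. When label effects differ by category, the planned moderation analysis has no overall test and no test of whether moderation varies by category. The unadjusted chance of a false claim per label, moderator and outcome goes from 5% to about 11-14%. Per-test power falls from 80% to about 48-71% if moderation is similar across categories. These ranges rest on an assumed ρ of 0.2 to 0.7 and on equal precision in the three categories.

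The missing category term in the pooled route is an inconsistency with the main model. It affects the log-odds interaction and the random-intercept SD, by amounts that depend on assumed category differences. ADE differences and z-values stay nearly the same, except that z-values can shift if the fitted intercept variance falls to zero.

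No primary or secondary result changes. Severity is low, and the change is a cheap improvement.

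**What to change.** In both routes, fit one random-intercept logistic model per outcome and moderator, with arm, category, moderator, all two-way interactions (including moderator-by-category) and the three-way term. Then report, in this order:

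1. One overall arm-by-moderator test per label. Define it as the contrast averaged over the three categories, because with the three-way term in the model a single arm-by-moderator coefficient refers only to the reference category.
2. A joint test of the three-way term, which addresses whether moderation differs by category.
3. Category-specific moderator differences in ADEs from the same model, as descriptive results.

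Label all of these exploratory.

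The cost is a change of wording in the Exploratory Analyses section before data collection. No further data are needed. The model has a few more parameters, and the overall test averages over categories, so it is weak if moderation is confined to one of them. The category-specific estimates remain available for that case.
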